8.1.2 Screening

Participants will be screened to review inclusion and exclusion criteria (see Appendix 2).

8.1.2.1 Screen Failures

Screen failures are defined as participants who consent to participate in the study but are not subsequently entered into the study. Individuals who do not meet the criteria for participation in this trial (screen failure) cannot be rescreened due to the timeline of intervention with respect to the radiation therapy.

8.1.3 Projected Participants

Recruitment will stop when 16 participants have completed the study.

8.2 Materials

8.2.1 Flyer

During clinic visits, the provider or research staff can introduce the study to participants and hand them a flyer (Appendix 3). Flyers may also be placed within the clinic, such as waiting rooms, reception desks, bulletin boards, and examination rooms. The flyer will include a brief description of the study, eligibility criteria, what participation involves, potential benefits, and risk, as well as contact details for more information.

8.2.2 Social Media

Not applicable.

9. STUDY PROCEDURES

9.1 Screening Visit

9.1.1 Informed Consent/Accent/HIPAA Authorization (Appendix 4)

The Informed Consent Process will take place at screening.

9.1.2 Review of Inclusion/Exclusion Criteria, Demographics and Medical History

9.1.3 Fatigue 0-10 Numeric Rating Scale

9.2 Participant Survey of Patient-Reported Outcomes and Information

All patient-reported outcomes and information (Appendix 5) will be collected using the web-based survey platform REDCap unless the participant prefers paper surveys, in which case paper surveys will be provided. Alternatively, a clinical

research coordinator may conduct the survey by interview either by phone or in person, based on participant preference. Web-based surveys can be completed on a tablet in the clinic or at home, with automatic email reminders sent through REDCap or by the research coordinator (see Appendices 5 and 6). Reminders will be sent 1 and 2 days after the initial survey invitation and 1 day before the survey window closes. The research coordinator may also reach out to participants by phone to remind them to complete the survey and provide verbal assistance as needed.

9.3 Study Intervention Visits

9.3.1 Enrollment

Enrollment would occur any time within 7 days (before or after) simulation, prior to the start of radiation. Items to be completed at enrollment:

- Randomization

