5.3 Allocation to Treatment Groups and Blinding/Randomization

Included subjects were randomly assigned in a 1:1 manner, stratified by baseline fatigue level, using computer-generated numbers. The PI and treating MD will be blinded to the randomization scheme; however, the ultimate allocation to the intervention will not be blinded.

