9.3.1.1 Height and weight

9.3.1.2 Patient-reported demographics/medical history (comorbidities)

- Stages of change metric

- All patients will be provided with a Fitbit device and provided detailed instructions on its use (Appendix 7). Data monitoring will start with the time that the Fitbit is provided to the patient after consents are signed and will continue to the end of study enrollment.

- The following baseline assessments are collected:

- FACIT-F
 - EPIC Bowel and Urinary short form assessments
 - PROMIS-29 QoL Metric
 - PROMIS Cognitive Function
 - PROMIS Self-Efficacy for Chronic Conditions
 - 6MWT

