10.2 Measures to Minimize Bias: Randomization / Blinding

Randomization will be utilized to allocate patients between early and delayed intervention arms. This study will be nonblinded to the patient given the nature of the intervention and nonblinded to the physician due to the nature of the clinical relationship, likely leading to a high chance of patient divulging of the participation in the intervention arm if they are randomized to the exercise coaching intervention. Bias with regard to patient factors will be minimized due to the use of randomization. Bias regarding the rate of activity due to Fitbit monitoring will be present in this study but assumed to be equal between the two groups as both usual care and the intervention groups will be given a Fitbit for monitoring and the use of an attention control check-ins in both intervention groups.

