 - a. Individual adherence to the physical activity monitor will be defined as wearing the activity tracker for at least 8 hours a day for 70% of the days in the study. Heart rate will be used to determine wear-time. We set an a priori goal of overall 70% participant adherence to the physical activity monitor, to be analyzed per cohort (6 of 8 participants in each arm demonstrating adherence as defined above).
- 5) Adherence to recommendation of 150 minutes per week of moderate physical activity:
 - a. Individual adherence to regular physical activity will be defined as meeting the recommendation of 150 minutes of moderate physical activity per week, based on the Physical Activity Guidelines for Americans developed by the U.S. Department of Health and Human Services (HHS). The target for participant adherence is set at an a priori goal of 70%.

The *resource and management* feasibility will be assessed based on the capacity of the exercise coach and research team to perform the required tasks of the protocol:

- 1) Adherence to the timeline of study procedures and human and data management issues that could potentially arise during a full-scale RCT will be tracked. Adherence to the study timeline for completion of required patient surveys and 6MWT as well as appropriate scheduling (patient attendance not required) of the exercise coaching sessions and follow-ups will be a proxy measurement of research resource and human data management acceptability. We set an a priori goal of 80% adherence.

Secondary Objective Analytical Plan

- 1) Changes in patient-reported fatigue, bowel/urinary toxicity, QoL, cognitive function, sexual function and satisfaction, and self-efficacy, as well as distance walked during 6MWT from baseline to pre-specified time points (end of RT, 5-7 weeks post RT, and 16-19 weeks post RT) within and between each group will be compared using two-sample t-test or Wilcoxon Rank Sum test when appropriate. Repeated measure models/linear mixed effect models may also be used to explore the changes in self-reported questionnaires over time among different treatment groups. Data will be analyzed based on the intention-to-treat principle and used to estimate treatment effect size for future trial design.
- 2) Prevalence of fatigue at baseline in the population of endometrial cancer patients receiving pelvic radiation therapy will be reported using data collected in the screening process.

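### Randomisation is listed ahead of the baseline questionnaires, stages-of-change metric and 6MWT at the enrollment visit, and nothing requires these baselines before the patient learns her arm

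*Protocol*

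**What the plan says.** Section 9.3.1 sets the window for the visit: "Enrollment would occur any time within 7 days (before or after) simulation, prior to the start of radiation". Under "Items to be completed at enrollment" the first entry is "Randomization". Height and weight, demographics and comorbidities, the stages-of-change metric and provision of the Fitbit follow. The list closes with "The following baseline assessments are collected", covering FACIT-F, EPIC bowel and urinary, PROMIS-29, PROMIS Cognitive Function, PROMIS Self-Efficacy and the 6MWT. Table 1 places all of these in one Enrollment column, with the randomisation row above the stages-of-change metric, every questionnaire and the 6MWT.

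On blinding, Section 5.3 conceals the scheme from the PI and treating physician but adds that "the ultimate allocation to the intervention will not be blinded". Section 10.2 says "This study will be nonblinded to the patient given the nature of the intervention".

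On survey timing, Section 9.2 says "Web-based surveys can be completed on a tablet in the clinic or at home", with reminders one and two days after the invitation.

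On use of the baselines, Section 12.2 compares changes "from baseline to pre-specified time points (end of RT, 5-7 weeks post RT, and 16-19 weeks post RT", within and between groups, and uses them to estimate an effect size for a later trial. Section 1.3 names readiness to change as a candidate moderator.

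**The concern.** A baseline does its job in a randomised comparison because it cannot depend on the arm. Once a woman knows whether she will be coached from the first week of radiation or only some weeks after it ends, her answers on fatigue, self-efficacy or readiness to change, and her effort on a walk test, may depend on that knowledge. Randomisation balances the patients, but it does not protect a measurement taken after disclosure. Section 10.2 relies on randomisation to limit bias from patient factors and does not address this route.

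At stake are the effect-size estimates for the follow-up study and the moderator exploration. The pilot also tests how to run the later randomised trial, so an order of procedures adopted here may be carried forward. A larger sample would not shrink a bias of this kind, and no later analysis can recover a pre-allocation baseline that was never taken.

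**Working it through.** The protocol states no figure on this point, so there is none to reproduce. The check sets the sections side by side.

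1. **Is an order stated?** Not expressly. Section 9.3.1 and Table 1 both list randomisation before the questionnaires, the stages-of-change metric and the 6MWT. They disagree on height and weight, which come after randomisation in 9.3.1 and before it in Table 1. The lists therefore cannot both be a strict sequence.

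2. **Does any section require baselines first?** No. Sections 5.3, 9.1, 9.2, 9.3.1, 10.1.1 and 10.2 contain no such condition.

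3. **Can the arm be known before the baseline is given?** Yes. Allocation is open (5.3, 10.2). Section 10.1.1 has the patient scheduled with the coach according to her assigned group once she has consented. Section 9.2 allows home completion with reminders on later days.

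4. **What does she learn?** Table 1 shows 25 fractions in five weekly blocks. Immediate start is in the first of them. Delayed start is 6 to 8 weeks after radiation, so 5 + 6 = 11 to 5 + 8 = 13 weeks after radiation begins.

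5. **Does randomisation need anything from the baseline battery?** No. The stratifier is the 0-10 fatigue rating (0-3 versus 4-10), which Table 1 and Section 9.1.3 place at screening.

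6. **Which analyses use these baselines?**
   - Fatigue, bowel/urinary toxicity, QoL, cognitive function, self-efficacy and 6MWT: the baseline battery is taken only at the enrollment visit, so all six are exposed.
   - Readiness to change: exposed if, as seems intended, it is taken from the stages-of-change metric.
   - Sexual function: first collected 5-7 weeks after radiation (9.3.5), so there is no baseline to affect.
   - Fatigue prevalence and stratification: both use screening data, so neither is exposed.
   - Primary feasibility criteria (12.2): none uses these scores.

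7. **How would a shift enter the result?** Let δ_B and δ_F be the between-arm differences in reporting or effort caused by knowing the arm, at baseline and at follow-up. The between-arm difference in change is then

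   observed = true + δ_F − δ_B.

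   With baselines completed before disclosure, δ_B = 0. With baselines after disclosure, δ_B may be non-zero in either direction. The protocol gives no value for δ_B or δ_F, nor any outcome SD, so the bias cannot be calculated.

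**The case against.** The strongest reply is that these lists are inventories. Nothing is numbered as a sequence, and the disagreement over height and weight shows that position is weak evidence of timing. That stands. A reader might infer that the protocol prescribes randomisation before baselines, but the text does not support this. It leaves the order open, and the finding is limited to what it permits.

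Second, Section 9.2 describes survey modes in general and does not say that baseline surveys are returned after the enrollment visit, while 9.3.1 counts them among that visit's items. That also stands, but home completion is not ruled out for baseline, and disclosure earlier in the same visit would be enough.

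Third, the harm may be small. Knowledge of the arm persists in an open trial, so a shift that also persists cancels in the formula above; the full baseline shift reaches the result only if δ_F = 0. Both arms eventually receive the same ten sessions, a Fitbit and attention calls. Section 5.1.1 states that the pilot has no hypothesis. With 8 per arm and complete data, the standard error of the between-arm difference is √(1/8 + 1/8) = 0.5 SD of the change score, so chance error in this pilot is likely to be large beside any plausible shift. All of this limits the consequence. It gives no reason to leave the order open, since it can be fixed at almost no cost.

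**Conclusion.** The point holds as an avoidable gap in procedure. The protocol permits baselines to be given after the patient knows her arm, and its two lists, if followed from top to bottom, would produce exactly that. Six outcome domains under secondary objective 1, and readiness to change as a moderator, are exposed. The conclusion rests on open allocation, the absence of any rule on order, and the assumption that self-report or walking effort can respond to knowing the arm.

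Two stronger inferences should be resisted. A reader might conclude that every secondary analysis is compromised; sexual function has no baseline, and fatigue prevalence uses screening data, so neither is touched. A reader might also want to express the bias as a share of the treatment effect; the protocol supplies neither a shift nor a target effect, so such a ratio would only divide one assumption by another. The primary feasibility conclusions do not depend on this point.

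**What to change.** In Section 9.3.1 and Table 1, place the baseline questionnaires, the stages-of-change metric and the 6MWT before randomisation. Add one sentence: allocation is generated and disclosed to the patient and staff only after all of these are complete. Align the position of height and weight in the two lists at the same time. Record the completion date of each baseline relative to disclosure, so that departures can be reported. Patients with a late baseline should not be excluded on that account, because this would select on an event after randomisation and shrink a sample of 16, against the intention-to-treat principle in Section 12.2.

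The cost is a reordered list, one sentence and a date field. No visit or assessment is added, and the stratifier is already in hand from screening. The one practical consequence is that randomisation waits for the last baseline item, within the enrollment window and before radiation starts. The tablet and coordinator-interview options already in Section 9.2 make same-visit completion possible.

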9.3.1.1 Height and weight

9.3.1.2 Patient-reported demographics/medical history (comorbidities)

- Stages of change metric

- All patients will be provided with a Fitbit device and provided detailed instructions on its use (Appendix 7). Data monitoring will start with the time that the Fitbit is provided to the patient after consents are signed and will continue to the end of study enrollment.

- The following baseline assessments are collected:

- FACIT-F
 - EPIC Bowel and Urinary short form assessments
 - PROMIS-29 QoL Metric
 - PROMIS Cognitive Function
 - PROMIS Self-Efficacy for Chronic Conditions
 - 6MWT

9.3.2 RT Simulation

Items to be completed at RT Simulation:

- Fitbit data will be collected on all patients.

9.3.3 Week 1-4 of pelvic RT (Fraction 1-20)

Items to be completed at weeks 1-4 of RT:

- Fitbit data will be collected on all patients.

9.3.4 Week 5 of pelvic RT (Fraction 21-25)

Items to be completed at week 5 of RT:

- Fitbit data will be collected on all patients.
- The following assessments are collected:

- FACIT-F
- EPIC Bowel and Urinary short form assessments
- PROMIS-29 QoL metric
- PROMIS Cognitive Function
- PROMIS Self-Efficacy for Chronic Conditions
- 6MWT

9.3.5 Week 5-7 Post-pelvic RT

Items to be completed at week 5-7 post RT:

- Fitbit data will be collected on all patients.
- The following assessments are collected:
 - FACIT-F
 - EPIC Bowel and Urinary short form assessments
 - PROMIS-29 QoL metric
 - PROMIS Cognitive Function
 - PROMIS Self-Efficacy for Chronic Conditions
 - 6MWT
 - PROMIS Brief Profile Sexual Function and Satisfaction (Female)

9.3.6 Week 16-19 Post-pelvic RT

Items to be completed at week 16-19 post-pelvic RT:

- Fitbit data will be collected on all patients.
- The following assessments are collected:
 - FACIT-F
 - EPIC Bowel and Urinary short form assessments
 - PROMIS-29 QoL metric
 - PROMIS Cognitive Function
 - PROMIS Self-Efficacy for Chronic Conditions
 - 6MWT
 - PROMIS Brief Profile Sexual Function and Satisfaction (Female)
- Satisfaction survey
- Recorded semi-structured exit interview with research PI (Appendix 8)

9.3.7 Weekly Exercise coach check-ins x 10 weeks

- Early intervention cohort: Check-in #1 (60 minutes) to occur during the first week of RT (Fx 1-5). Check-in #2-10 (30 minutes) will continue weekly starting Fx 6-10, and continue through the completion of RT and post-RT for a total of 10 sessions.
- Delayed intervention cohort: Check-in #1 (60 minutes) to occur after the 5-7 week follow-up starting 6-8 weeks after pelvic-RT. Check-in #2-10 (30 minutes) will continue weekly a total of 10 sessions.

9.3.8 Bi-weekly active attention control check-ins x 10 weeks

- Early intervention cohort: Check-ins, once every 2 weeks, with an approximately 5-minute telephone call by a research coordinator to start the week following completion of their exercise intervention (approximately 5 weeks after pelvic RT) for a total of 5 calls.
- Delayed intervention cohort: Check-ins, once every 2 weeks, with an approximately 5-minute telephone call by a research coordinator starting during the first week of RT (Fx 1-5) and continue for 10 weeks for a total of 5 calls.
- The research coordinator will inquire about their use of the Fitbit device, such as if they are wearing it regularly, any technical issues, and if they are syncing their data without discussing physical activity.

9.4 Unscheduled Visits

We do not expect any unscheduled visits, but if the physician of record needs additional assessments, then these would be unrelated to the study intervention unless there is an indication that they would no longer be fit for participation in the research study due to an unanticipated change in status or patient circumstances.

9.5 Non-compliance and Lost to Follow-Up

The following actions must be taken if a participant fails to return to the clinic for a required study visit:

- 9.5.1 The adherence to the Fitbit will be routinely monitored during exercise check-ins or during the active-monitoring check-ins and data will be recorded for analysis using the PittBit dashboard. Email reminders may be sent to participants who are found not to be wearing their Fitbit as instructed (see Appendix 6).
- 9.5.2 For missed visits, the site will attempt to contact the participant and reschedule the missed visit and discuss with the participant the importance of maintaining the assigned visit schedule and ascertain if the participant wishes to and/or should continue in the study.
- 9.5.3 Before a participant is deemed lost to follow-up, the investigator or designee will make every effort to regain contact with the participant (where possible, 3 telephone calls and, if necessary, a certified letter to the participant's last known mailing address or local equivalent methods). These contact attempts should be documented in the participant's medical record or study file.
- 9.5.4 Should the participant continue to be unreachable, he/she/they will be considered to have withdrawn from the study with a primary reason of lost to follow-up.
- 9.5.5 Definition of Non-compliance: A patient will be considered non-compliant to the exercise coaching intervention arm if they fail to engage in 70% of the weekly check-ins. A patient will be considered non-compliant to the

physical activity monitor if they do not wear the Fitbit activity tracker for at least 8 hours a day for 70% of the days in the study. As this is a pilot study, patients will not be removed from study due to non-compliance, as the primary outcome is to evaluate adherence.

10. STUDY ADMINISTRATION

10.1 Study Intervention(s) Administration

10.1.1 Study Intervention Description

The intervention is an exercise coaching program which will consist of weekly check-ins for 10 weeks with a certified exercise coach with expertise in caring for oncology patients. The purpose of each check-in is to address readiness for exercise, identify barriers, and develop an individualized plan for exercise for the week with a goal of increasing activity to 150 minutes of moderate activity per week using any form of activity that is enjoyable and accessible to the patient. This will be accomplished by shaping behavior through personalized recommendations. Patients will be randomized to either an immediate- or delayed-start of their exercise coaching program. Women randomized to the immediate-start group will start the intervention during the first week of radiation therapy and continue through and post-completion of radiation. Women randomized to the delayed-start group will start the intervention at 6-8 weeks post-radiation, a more typical period in survivorship where exercise counseling may begin. Participants will be asked to wear an activity monitor to track steps and moderate activity minutes and to complete assessments of patient-reported cancer-related fatigue, bowel/urinary toxicity, sexual health, and quality of life and participate in a six-minute walk test (6MWT) at predefined time points throughout the study.

Once a participant consents to the research study, they will be scheduled with the exercise coach based on their treatment group assignment (immediate or delayed start). The exercise coach will record the participation in the Epic chart, which will automatically send a message via Epic (MyChart) to the participant with instructions for their first session (Appendix 9). The participant will be asked to complete an intake form to provide the exercise coach with necessary information for their first meeting (Appendix 10). After each of the 10 coaching sessions, the exercise coach will document the encounter in Epic using the Subjective, Objective, Assessment, Postural Assessment and Observations template (SOAP; Appendix 11).

10.1.2 Study Intervention Materials

All enrolled patients will be provided with resistance bands that can be utilized for a number of exercise classes that they might be referred to by their exercise coach. All participants will receive a de-identified Fitbit device for active minute tracking. Patients will be able to keep their

resistance bands and Fitbit device after completion of the study. The device will be unregistered from the de-identified account used for study participation, and patients will be able to create their own accounts to continue to use their devices at their discretion.

10.1.3 Dosing and Administration

Not applicable.

10.2 Measures to Minimize Bias: Randomization / Blinding

Randomization will be utilized to allocate patients between early and delayed intervention arms. This study will be nonblinded to the patient given the nature of the intervention and nonblinded to the physician due to the nature of the clinical relationship, likely leading to a high chance of patient divulging of the participation in the intervention arm if they are randomized to the exercise coaching intervention. Bias with regard to patient factors will be minimized due to the use of randomization. Bias regarding the rate of activity due to Fitbit monitoring will be present in this study but assumed to be equal between the two groups as both usual care and the intervention groups will be given a Fitbit for monitoring and the use of an attention control check-ins in both intervention groups.

